13.3. General Considerations

Continuous endpoints will be summarized with number (n), mean, standard deviation (SD), median, minimum, and maximum. In addition, change from baseline values will be calculated at each time point and summarized descriptively. For categorical endpoints, descriptive summaries will include counts and percentages.

All data supporting the development of the summary tables and figures will be listed.

13.4. Demographics and Baseline Characteristics

Demographics and baseline characteristics (age, sex, race, ethnicity, body weight, height, and BMI) will be summarized for the SS as well as the FAS separately. No formal statistical comparison between the groups will be performed.

Medical history will be listed by subject.

Pregnancy test results and drug/alcohol screens will be listed but not summarized.

13.5. Pharmacodynamic Analyses

All PD analyses will use the FAS Set.

The FAS will be used for the primary analysis. Summary statistics will be provided (mean, standard deviation, median, minimum, maximum) for each treatment. Figures will be provided for the within-subject difference scores by treatment and day as both a histogram and scatter plot. Data listings for driving simulator data will be provided.

SDLP data will be analyzed using a mixed model for repeated measures (MMRM) with fixed effects for sequence, period, and treatment and random effect for subject. A log-transformation of SDLP values to obtain normal distribution of data will be considered, if necessary. An unstructured covariance structure and Kenward-Roger degrees of freedom will be used. In the event an unstructured covariance structure fails to converge, a variance components covariance structure will be assumed. In addition to treatment effect, p-values for significance testing of period and sequence effects will be provided. Pair-wise comparisons of differences in means and two-sided 95% CIs on differences will be provided for all active treatments versus the placebo treatment.

The comparison of primary interest is cannabis versus placebo on Day 2 as a function of frequency of self-reported cannabis use. The statistical significance of alprazolam versus placebo ($p < 0.05$) comparison for SDLP is considered only to validate the experiment and having the ability to detect effects (i.e., assay sensitivity).

Formal statistical tests (when performed) will be 2-sided and tested at the $\alpha=0.05$ level of significance. Cannabis will be considered non-inferior to placebo if the two-sided upper 95% confidence limit on the difference in SDLP between that dose and placebo is less than 4.4 cm, and it can be concluded that the effect of cannabis on driving is less than that seen at 0.05% BAC, which is a level associated with increased crash risk. No adjustment to alpha levels will be made for either the comparison of alprazolam to placebo, or for secondary endpoints or analyses.

As a supportive analysis, pair-wise, within-subject differences in SDLP greater than 4.4 cm in absolute value will be compared using McNemar test. Furthermore, these pair-wise, within subject differences in SDLP will be tested for symmetry about zero (Laska et al., 2012) using the maximally selected McNemar test. If there is no significant difference between placebo and cannabis and if the distribution of paired differences is symmetrical around zero, it can be concluded that cannabis does not impair driving.

Driving performance, cognitive, and self-report endpoints will be evaluated and presented using a mixed model for repeated measures. Lane exceedance will be log-transformed (more specifically $\ln[x+1]$) before analyses.

A data listing for the results will be provided. Summary tables will be presented in the same format as the primary output for:

- Driving Performance Endpoints
 - SDLP
 - Lane exceedance; including number, maximum and duration of exceedance
 - Speed related measures; including speed deviation, average speed, and excessive speed count
 - Driving safety measures; including excessive Ay (cornering speed threshold-exceeded), and total number of collisions
 - Divided attention measures; including correct responses, omission errors, commission errors, reaction time, and standard deviation of reaction time

- CogScreen SDC Test
 - Number of correct responses
 - Response accuracy
 - Standard deviation of reaction time
- CogScreen Symbol Digit Coding – Immediate Recall
 - Immediate recall accuracy
- CogScreen Symbol Digit Coding – Delayed Recall
 - Delayed recall accuracy
- CogScreen Visual Sequence Comparison Test
 - Response speed
 - Response accuracy
 - Standard deviation of reaction time
- CogScreen Divided Attention Test
 - Response speed
 - Number of premature responses
 - Response accuracy
 - Number of lapses
 - Multitasking scores
- CogScreen Matching To Sample Test
 - Response speed
 - Response accuracy
 - Standard deviation of reaction time
- CogScreen Pathfinder Number
 - Response speed
 - Response accuracy
 - Response coordination
- CogScreen Shifting Attention Test
 - Response speed
 - Response accuracy
 - Standard deviation of reaction time
- CogScreen Dual Task Test
 - Tracking errors
 - Number of boundary hits
 - Previous number response speed
 - Previous number response accuracy
 - Previous number standard deviation of reaction time
 - Multitasking scores

- Test of Variables of Attention (TOVA)
 - Response time variability (Total, and Scores per quarter)
 - Response speed (Total, and Scores per quarter)
 - Commission errors (Total, and Scores per quarter)
 - Omission errors (Total, and Scores per quarter)
- KSS
- Self-Reported Readiness to Drive
- VAS to assess subject's motivation and self-appraisal of their driving performance, including readiness to drive and whether the subject feels safe to drive

For total number of collisions, differences in number of collisions for each pair-wise comparison will be provided with their corresponding Wilcoxon Signed Rank p-value. A bar chart will be provided pooling total number of collisions by 0, 1, 2, or ≥ 3 for all treatments. In addition, pair-wise treatment comparisons for readiness to drive will be analyzed using McNemar's test. A bar graph for percentage of subjects reporting no safe to drive will be provided by treatment and day.

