Subjects will be discharged from NADS on the afternoon of Day 2 of each period approximately 5.33 hours post-dose, provided they are medically stable for discharge in the opinion of the Investigator based on the criteria established by the medical monitor. The subject will not be able to drive themselves home and will have transportation arranged.

After a washout of at least 7 days and no more than 10 days between administration of the last dose in one period and administration of the first dose in the next period, subjects will be readmitted to NADS on Day 1 of Period 2 and receive study drug according to the assigned treatment schedule. All study assessments will remain the same as in Period 1. The same process will be repeated for Period 3.

Seven days (± 2 days) after discharge from Period 3, subjects will receive a follow-up/end-of-study phone call from the site to evaluate the presence of any AEs and collect any new concomitant medication/procedure information.

Figure 1. Study Design

The schedule of assessments is provided in [Table 1](#).

The following regimens will be assessed:

- Treatment A: cannabis (inhaled)
- Treatment B: alprazolam 0.75 mg PO
- Treatment C: placebo PO
- Subjects receive 1 tablet of alprazolam and/or matched placebo 40 minutes prior to administration of inhaled cannabis/or matching placebo on Day 2 of each treatment period.

Treatment Sequences

Sequence	1	2	3
1	A	B	C
2	B	C	A
3	C	A	B
4	A	C	B
5	B	A	C
6	C	B	A

Number of Subjects (planned): Approximately 12 subjects will be randomized and dosed to target 6 - 8 subjects completing the 3 treatments. Efforts will be made to randomize an approximately equal number of subjects by gender. Efforts will be made to randomize an approximately equal number of “low frequency” users (1-10 uses per month) and “high frequency” users (>20 uses per month).

Eligibility Criteria:

Inclusion

1. Subject understands and provides written informed consent prior to the initiation of any protocol-specific procedures.
2. Subject is able to comprehend and willing to comply with the requirements of the protocol.
3. Subject is a healthy male or female, 19 to 45 years of age, inclusive, at Screening.
4. Subject has a regular sleep pattern (usual bedtime between 21:00 and 00:00).
5. Subject has Score <10 on Epworth Sleepiness Scale at Screening.

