7. INVESTIGATIONAL PLAN

7.1. Overall Study Design

This is a randomized, double-blind, active- and placebo-controlled, 3-arm, 3-period crossover study to assess the effects of cannabis on simulated driving performance and related cognitive functions in healthy male and female adult cannabis users. The study design is provided in Figure 1. The schedule of assessments is provided in [Table 1](#).

Following a screening/training period of up to 14 days, eligible participants will be admitted to NADS on Day 1 of Period 1. Baseline performance for cognitive testing will be obtained and subjects will practice the CRCDS2-MiniSim driving simulator. Participants will be randomized 1:1:1 into one of 6 treatment sequences as shown in Table 4. Study drug will be administered by inhalation on Day 2 with the alprazolam dosing approximately 40 minutes prior to the cannabis dosing (the first cannabis dose will occur at approximately 8:40); precise timing is relative, as subject dosing will be staggered/offset to accommodate staffing and subject flow. Blood samples for pharmacokinetic analysis will be drawn pre-dose and again 40 minutes post-dose and 3.25 hours post-dose. Symbol Digit Coding (SDC), Pathfinder Number (PFN), Readiness to Drive Question, and the Karolinska Sleepiness Scale (KSS) will be administered approximately 30 minutes post-dose. A baseline KSS will also be administered prior to dosing. Driving assessments will begin approximately 45 minutes following dosing. Driving performance will be assessed via the approximate 1-hour Drug Impaired Driving Scenario (DIDS), on the CRCDS2-MiniSim driving simulator, comprised of suburban, urban and highway driving tasks. The scenario includes challenges designed to assess lane position control, speed control, safety awareness and responsivity, driving-related decision making, multitasking, and vigilance. Immediately after completing the driving simulation, subjects will be administered the visual analog scales, or VAS, followed by the cognitive test battery (SDC, Visual Sequence Comparison [VSC], Divided Attention Test – Dual [DAT-Dual], PFN, SDC Delayed Recall [SDCDR], Shifting Attention Test – Instruction [SAT-Instruction], MTS, Dual Task Test – Combined [DAT – Combined], and TOVA). At approximately 3.5 hours post-dose the cognitive test battery (i.e., SDC, VSC, DAT-Dual, PFN, SDCCDR, SAT – Instruction, MTS, DTT – Combined, TOVA) and self-report measures will be repeated.

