9. TREATMENT OF SUBJECTS

9.1. Study Drugs

Cannabis will be administered via vaporizer for an inhaled dose of 30.9mg THC on Day 2 during Treatment Period A. Alprazolam tablets at a dose of 0.75mg will be administered orally in Treatment Period B approximately 40 minutes earlier on Day 2. Matching placebo (i.e., inhaled via vaporizer or tablets, dependent on Treatment Period) will be administered during Treatment Period C. Subjects will receive active or matched placebo each morning during each Treatment Period. Placebo will be administered as necessary to maintain the blind across the 3 periods. Dosing for each treatment is outlined in [Table 4](#).

Table 4: Treatments Administered

Treatment	Study Drug	Day 2
A	Cannabis	30.9mg THC
B	Alprazolam	0.75mg
C	Placebo	Placebo

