10.5. Study Drug Administration

A cued-puff procedure will be used to standardize the administration of cannabis. Dried bulk cannabis plant material obtained from the NIDA Drug Supply Program is ground (via herb mill/grinder provided by Volcano® manufacturer) and 500 mg is heated to a temperature of 210°C by the hot air generator to vaporize THC (Hazekamp, 2010; Pomahacova et al., 2009). The vapor is collected in a plastic balloon with a one-way valve. This valve shuts when removed

from the Volcano® device, preventing the escape of vapor. A mouthpiece is attached to the valve and allows for subject-controlled inhalation of the cannabis vapor. Each session utilizes a new balloon to ensure hygienic administration. The Volcano® Digit Vaporizer is operated according to the manufacturer's specifications.

Subjects will be trained to the Foltin Puff Procedure (Foltin, Brady & Fischman, 1986; Wilsey et al., 2013), which includes the following steps: "get ready" (5 seconds), "inhale" (5 seconds), "hold vapor in lungs" (10 seconds), and "exhale and wait" (40 seconds). The subject repeatedly inhales the vapor over 10 minutes. Subjects will be instructed to inhale at their capacity; that means without any dizziness, nausea, vomiting, panic, or difficulty breathing.

All study treatments will be administered following consumption of breakfast as outlined in Section 9.2.

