13.1. Data Analysis Sets

The Randomized Set is defined as all subjects who are randomized.

The Full Analysis Set (FAS) is defined as all randomized and treated subjects that have at least one primary efficacy measure (SDLP) in any treatment period.

The Safety Set (SS) is defined as all subjects administered at least one dose of any study drug.

The PK Set is defined as all subjects in the SS who have at least one collected blood sample from which a valid blood concentration can be measured.

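### The 4.4 cm non-inferiority conclusion rests on the Full Analysis Set alone, with no supportive analysis confirming that the cannabis-placebo exposure contrast was delivered

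*Combined protocol and SAP*

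**What the plan says.** - **Analysis set.** Section 13.5: "All PD analyses will use the FAS Set". Section 13.1 defines the FAS as "all randomized and treated subjects that have at least one primary efficacy measure (SDLP) in any treatment period". The other sets are Randomized, Safety and PK. None carries an adherence or exposure condition.
- **Decision rule.** Section 13.5 declares cannabis non-inferior to placebo if the two-sided "upper 95% confidence limit on the difference in SDLP between that dose and placebo is less than 4.4 cm". From this it draws the conclusion that the effect is smaller than at 0.05% BAC. A supportive McNemar and symmetry analysis, also on the FAS, can lead to the further statement that cannabis leaves driving unimpaired.
- **Exposure.** Section 9.1 describes cannabis given by vaporizer "for an inhaled dose of 30.9mg THC". Section 10.5 describes a cued-puff procedure over 10 minutes with inhalation under the subject's control: "Subjects will be instructed to inhale at their capacity", where capacity is defined by the absence of listed unpleasant effects.
- **THC data collected.** The urine screen includes THC (12.1.5.1) and is scheduled at Screening and on Day 1 (Table 1). Blood is drawn pre-dose and at 40 minutes and 3.25 hours on Day 2 (11.2.1).
- **Use of those data.** A THC-positive urine test is exempt from the exclusion (8.2, item 13). Screen results are listed only (13.4). Blood THC is listed, summarized and entered in a regression with no stated model (13.7).
- **Size.** The Synopsis says: "Approximately 12 subjects will be randomized and dosed to target 6 - 8 subjects completing the 3 treatments".

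**The concern.** In a superiority comparison, keeping every treated subject is the cautious choice, because a period that failed to deliver treatment works against finding a difference. In a non-inferiority comparison the same period works in favour of the conclusion. A cannabis period in which the subject took in little THC looks like a placebo period and moves the estimated difference toward zero.

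The figure of 30.9 mg is the THC content of the 500 mg loaded, yet the non-inferiority statement is worded as a conclusion about that dose. If absorbed exposure was materially lower in some periods, a pass would partly reflect under-exposure. At stake is a public-safety statement that the effect of cannabis on driving is below that of 0.05% BAC. The alprazolam comparison does not protect against this: it shows that the simulator can detect an oral drug's effect and says nothing about whether cannabis was absorbed.

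**Working it through.** The documents give no SD, power, expected difference or dropout rate, so there is no sponsor calculation to reproduce.

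**Inputs from the documents**
- Margin 4.4 cm, applied to the upper limit of a two-sided 95% interval, i.e. one-sided 2.5% (13.5).
- 12 randomized, 6 to 8 completers (Synopsis).
- Three-period crossover, so the contrast is within subject (7.1).
- THC loaded: 500 mg × 6.18% = 30.9 mg (5.2).

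**Assumptions, not in the documents**
- SD of within-subject SDLP differences: 3 to 6 cm.
- Number of subjects *k* with no cannabis-placebo contrast: 0 to 3.

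**Step 1: shift in the mean.** If *k* of *n* subjects have zero contrast and the rest have true effect δ, the expected difference is δ × (1 − k/n). With δ = 4.4 and n = 8:
- k = 1: 4.4 × 7/8 = 3.85 cm
- k = 2: 4.4 × 6/8 = 3.30 cm
- k = 3: 4.4 × 5/8 = 2.75 cm

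**Step 2: effect on the decision.** The rule uses the confidence limit, and the mixture of exposed and unexposed subjects also widens the interval, so the mean alone does not settle the matter. The rule was simulated as mean + t(0.975, n−1) × s/√n < 4.4, with 200,000 runs per cell, as a paired stand-in for the planned mixed model. False-pass rates with a true effect of 4.4 cm, as ranges over SD 3 to 6 cm:

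| n | k = 0 | k = 1 | k = 2 | k = 3 |
|---|---|---|---|---|
| 6 | 2.5% | 3.8–4.3% | 5.8–8.1% | 9.2–16.1% |
| 8 | 2.5% | 3.7–4.4% | 5.5–7.9% | 8.1–14.3% |
| 12 | 2.5% | 3.6–4.3% | 5.1–7.4% | 7.1–12.2% |

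The wider interval offsets part of the bias, but the net movement is toward passing in every cell. With the affected subjects removed, the rate returns to about 2.5%, provided that removal is unrelated to outcome.

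**Step 3: partial exposure in everyone.** At n = 8, if all subjects show 90% of a 4.4 cm effect, the false-pass rate is 3.8–5.5%. At 75% it is 6.6–14.5%.

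**Step 4: effects above the margin.** With a true effect of 6.0 cm, n = 8 and k = 2, the false-pass rate is 0.4–1.6%. With a true effect of 5.0 cm it is about 1.4–2.2% (1 of 8 unexposed), 2.1–2.7% (2 of 12) and about 4% (3 of 12). The problem is concentrated near the margin.

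**The case against.** **The plan does standardize and observe exposure.** Puffs are cued and timed, subjects are trained, dosing and any non-adherence are recorded (9.4), and blood THC is regressed against SDLP and listed by subject (13.7). A reader might infer that nothing in the plan would reveal under-exposure. That goes too far: weak periods would be visible. What stands is that none of this is tied to the 4.4 cm decision.

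**Abstinence is checked.** A reader might infer that abstinence from non-study cannabis goes unverified. The documents do not support this: THC is measured in urine on Day 1 and in blood before dosing, and subjects are under supervision from the afternoon before dosing (Appendix B). The gap is the absence of an analysis rule that uses these results.

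**Direction is not fixed for every breach.** It is tempting to say that non-study cannabis use also favours passing. It does so only if it raises SDLP before the placebo period or blunts the response to study cannabis. Residual effect before the cannabis period pushes the other way, and equal residuals cancel. Low inhalation is the mechanism with a clear direction.

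**A diluted mean under 4.4 cm is not a pass.** An assumed 5.0 cm effect with 1 of 8 subjects unexposed averages 5.0 × 7/8 = 4.375 cm, which looks like a pass. The rule needs the upper limit below 4.4 cm, and that scenario passes only about 1.4–2.2% of the time.

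**A stricter set could do harm.** Subjects who stop at capacity are following the protocol, so an ordinary per-protocol set would keep those periods. Requiring a complete puff session could instead drop people who stopped because of strong effects, which might make non-inferiority easier. With 6 to 8 completers and selection after randomization, making a second set a mandatory condition for the claim is a debatable trade-off. This objection stands and limits the remedy to a supportive analysis.

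**The primary objective is detection (6.1).** For that aim the FAS is the cautious set. This also stands.

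**Conclusion.** The point holds in a limited form. The non-inferiority conclusion, and the further statement of no impairment, are drawn from the FAS alone, and no analysis checks that the exposure contrast was delivered. Under-exposure in cannabis periods biases both toward a favourable reading.

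For a true effect at the margin and 8 subjects, the false-pass rate rises from 2.5% to about 4% with one unexposed subject and to about 6 to 8% with two. These figures depend on the assumed SD of 3 to 6 cm, the assumed number of unexposed subjects and a paired approximation to the planned model. The inflation shrinks quickly as the true effect moves above 4.4 cm.

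The documents do not show that under-exposure will occur, only that the procedure allows it and the non-inferiority analysis takes no account of it. They do not support a claim that the FAS is the wrong primary set or that non-inferiority should have to be met in two sets. This is a cheap improvement to a secondary conclusion and leaves the detection analysis as it is.

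**What to change.** Keep the FAS as the primary set. Add to 13.1 and 13.5 one supportive, period-level SDLP analysis with the same model, specified as follows:

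1. Include periods with a completed drive and with pre-dose and 40-minute blood THC consistent with the assigned treatment.
2. Fix the THC criteria before unblinding, and allow for residual THC in frequent users so that they are not excluded for their baseline level.
3. Do not exclude a subject for stopping inhalation because of drug effects. Stopping at capacity is not non-adherence under 10.5, so the dosing record in 9.4 should capture the reason.
4. Report the 4.4 cm comparison in both sets. If they disagree, qualify the non-inferiority statement and the statement of no impairment.

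Sections 9.1 and 10.5 should also be reconciled on whether 30.9 mg denotes THC loaded or THC inhaled.

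**Cost.** One definition and one extra model run, with blood samples already planned. The interval will be wider in a smaller set selected after randomization, which is why this analysis supports the FAS and does not replace it.

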- 25. Subject participates in night shift work.
- 26. Subject has traveled across ≥ 1 time zone in the 2 weeks prior to Admission for Period 1 or is expected to travel across ≥ 1 time zone during the study.
- 27. Subject is investigative site personnel or their immediate families (spouse, parent, child, or sibling whether biological or legally adopted).

Study Drug Dosage and Mode of Administration: Cannabis will be administered by inhalation.

Reference Therapy, Dosage and Mode of Administration:

Alprazolam (active comparator) at a dose of 0.75 mg will be administered orally.

Cannabis matching placebo will be administered by inhalation.

Alprazolam matched placebo will be administered orally.

Duration of Treatment:

Subjects will receive 1 500 mg dose of cannabis active on Day 2 of one of the three periods.

Subjects will receive 1 dose of alprazolam 0.75 mg active on Day 2 of one of the three periods.

Subjects will receive placebo in all treatments.

Subjects will not receive active cannabis and alprazolam during the same period.

Statistical Methods:

A statistical analysis plan (SAP) will provide a detailed description of the analyses to be performed in the study. The SAP will be finalized and approved prior to database lock. Any deviations from or changes to the SAP following database lock will be described in detail in the clinical study report.

Analysis Sets

Randomized Set: All subjects who are randomized

Full Analysis Set (FAS): all randomized and treated subjects that have at least one primary efficacy measure (SDLP) in any treatment period.

Safety Set (SS) will include all subjects administered at least one dose of any study drug.

PK Set will include subjects in the Safety Set who have at least one collected blood sample from which a valid blood concentration can be measured.

Primary analysis

The FAS will be used for the primary analysis.

The comparison of primary interest is cannabis versus placebo (Day 2) as a function of frequency of self-reported cannabis use. The statistical significance of alprazolam versus placebo ($p < 0.05$) comparison for SDLP is considered only to validate the experiment as having the ability to detect effects (i.e., assay sensitivity).

Formal statistical tests (when performed) will be 2-sided and tested at the $\alpha = 0.05$ level of significance.

Secondary Analyses

The FAS will be used for secondary analyses.

Safety Analyses

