PURPOSE OF PRESENT STUDY: The primary purpose of the current study is to establish a standardized protocol for assessing drug impaired driving. Validation of this methodology is to be accomplished with a study using cannabis, alprazolam, and matching placebo. As part of this research effort, investigators have worked to identify the driving tasks and cognitive abilities found to be most vulnerable to the impairing effects of cannabis. In addition, an effort was made to identify the subject characteristics associated with increased vulnerability to the impairing effects of cannabis. Worked was conducted to develop a methodology for determining when drivers are safe to resume driving after drug exposure. The current study is designed to test these hypotheses.

Simulated driving will be performed using an updated version of Cognitive Research Corporation's Driving Simulator (CRCDS2 MiniSim). The prior version of this simulator has been used in dozens of driving studies submitted for regulatory review. Driving performance will be assessed using an approximate 1-hour Drug Impaired Driving Scenario (DIDS), comprised of suburban, urban and highway driving tasks. The scenarios include challenges designed to assess lane position control, speed control, safety awareness and responsivity, driving-related decision making, multitasking, and vigilance. These domains correspond to the Essential Driving Ability

Domains described by Kay and Logan (2011). In addition, cognitive functions associated with driving performance and self-report measures will also be administered.

Consistent with the principles outlined in the FDA Guidance for Industry (2017), this study includes both a positive (active) and placebo control condition. The study is designed to assess the duration of drug effects. Readiness to resume driving will be assessed using both self-report and objective testing. Subjects will include regular (daily) users and weekly users of cannabis. The intent is to assess the impact of pattern of drug use on driving performance. A cross-over study design will be utilized to maximize statistical power.

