6. STUDY OBJECTIVES AND ENDPOINTS

6.1. Study Objective

The primary objective of this study is to validate the DIDS scenarios using the CRCDS-2 driving simulator, by assessing the acute effects of cannabis relative to placebo on simulated driving performance. Assay sensitivity will be demonstrated by the significant effect of alprazolam 0.75 mg on driving and cognitive endpoints. A secondary objective of the study is to assess the effects of cannabis on cognitive and psychomotor functioning relative to placebo. Another objective of this study is to evaluate the potential relationship between THC blood concentration and driving performance endpoints.

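### Section 13.5 names the cannabis effect by frequency of use as its primary comparison, but its SDLP model has no frequency term and cannot estimate it

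*Combined protocol and SAP*

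**What the plan says.** Section 13.5 states: "The comparison of primary interest is cannabis versus placebo on Day 2 as a function of frequency of self-reported cannabis use". The Synopsis, under Primary analysis, says the same: "The comparison of primary interest is cannabis versus placebo (Day 2) as a function of frequency of self-reported cannabis use". Section 5.1 explains why two kinds of user are enrolled: "The intent is to assess the impact of pattern of drug use on driving performance". Section 8.1 defines the groups as 1-10 and more than 20 uses per month, and section 7.2 aims for roughly equal numbers of each.

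The SDLP model in 13.5 is a "mixed model for repeated measures (MMRM) with fixed effects for sequence, period, and treatment and random effect for subject". It is to report each active treatment against placebo, with p-values for period and sequence as well as treatment. The non-inferiority rule requires the "two-sided upper 95% confidence limit on the difference in SDLP between that dose and placebo is less than 4.4 cm". As support, "pair-wise, within-subject differences in SDLP greater than 4.4 cm in absolute value will be compared using McNemar test", followed by a symmetry test on the same differences. On multiplicity: "No adjustment to alpha levels will be made for either the comparison of alprazolam to placebo, or for secondary endpoints or analyses".

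The primary objective in section 6.1 is to validate the scenario "by assessing the acute effects of cannabis relative to placebo on simulated driving performance", without mention of use frequency. Section 13 leaves detail to a separate SAP, which was not among the documents supplied.

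**The concern.** An effect as a function of use frequency is either a treatment-by-frequency interaction or a pair of group-specific differences. The model in 13.5 contains neither, and nothing else in section 13 supplies them: the summaries, contrasts, 4.4 cm rule, McNemar and symmetry tests, and collision and readiness analyses are all by treatment only. A random subject effect or a sequence effect cannot stand in for the interaction, and a frequency main effect alone would not do so either.

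Two things are at stake. The named primary comparison would go unreported. In addition, two candidate primary estimates, pooled and group-specific, would remain open, with no rule saying which one the 4.4 cm limit applies to. If that is still unsettled at unblinding, the choice can follow the data.

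**Working it through.** The plan states no power, SD or sample-size calculation, so there is no figure of its own to reproduce. The structural point needs no assumption; the precision figures do.

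**1. What the model can estimate.** Take the six sequences with one low- and one high-frequency user in each (36 observations). The fixed effects in 13.5 have rank 10. Adding frequency (1 df) and treatment by frequency (2 df) raises the rank to 13. Noise-free cannabis effects passed through both models give:

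| True effect, low / high users (cm) | Cannabis minus placebo, 13.5 model | High minus low, with interaction |
|---|---|---|
| 6 / 0 | 3.0 | -6 |
| 5 / 1 | 3.0 | -4 |
| 3 / 3 | 3.0 | 0 |

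The 13.5 model cannot tell these three situations apart.

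**2. Precision.** From the documents: about 12 randomized with 6-8 completers targeted (Synopsis), two-sided alpha 0.05 and the 4.4 cm limit (13.5). Assumed: SD of paired SDLP differences 3 to 8 cm, equal groups, completers only, periods balanced over treatments, and the variance-components structure that 13.5 names as its fallback. With N completers, the error df are 2N-4 for the terms in 13.5 and 2N-6 once treatment by group is added. The 95% half-widths are:

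- pooled: t × SD/√N
- one group: t × SD/√(N/2)
- interaction: t × SD × √(4/N)

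For N = 8 and SD = 3: pooled 2.179 × 3/2.828 = 2.31 cm; group 2.228 × 3/2 = 3.34 cm; interaction 2.228 × 3 × 0.707 = 4.73 cm. At SD = 8 they are 6.16, 8.91 and 12.60 cm.

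| Completers | Pooled (cm) | One group (cm) | Interaction (cm) |
|---|---|---|---|
| 12 | 1.8-4.8 | 2.6-6.9 | 3.6-9.7 |
| 8 | 2.3-6.2 | 3.3-8.9 | 4.7-12.6 |
| 6 | 2.8-7.5 | 4.2-11.3 | 6.0-16.0 |

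**3. Chance that the upper limit is below 4.4 cm when the true effect is 0.** Noncentral t for the pooled and one-group columns, simulation for both groups; each cell runs from SD 3 to SD 8.

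| Completers | Pooled | One given group | Both groups |
|---|---|---|---|
| 12 | 99.8%-44% | 92%-25% | 86%-7% |
| 8 | 97%-30% | 75%-17% | 57%-4% |
| 6 | 88%-22% | 57%-12% | 38%-3% |

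**4. Can pooling hide a harmful group effect?** True effects of 7 and 0 cm average (7 + 0)/2 = 3.5 cm, below 4.4 cm. In simulation with 8 completers the pooled rule is met in only about 2% to 4% of trials, because the interval is wide.

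**5. Error rate if groups decide.** With both true effects at 4.4 cm, a rule that lets either group pass is met in about 5% of simulated trials, against 2.5% for one group. A rule requiring both is met in about 0.1% to 0.2%.

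**The case against.** The strongest reply is that the primary objective and the key endpoint concern cannabis against placebo without reference to frequency, and the 13.5 model estimates exactly that. On this view only a qualifying phrase goes unserved, and with 6-8 completers the interaction interval is wider than the 4.4 cm margin across the assumed SD range, so adding the term would settle little. The detailed SAP might also add it.

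Part of this stands. The objective does not demand a frequency analysis, the group estimates would be imprecise, and the risk of a false non-inferiority claim in the 7/0 example is small. Those points favor letting the pooled difference decide; they do not reconcile 13.5 with itself. The phrase is no slip: it appears twice as the comparison of primary interest, and enrollment is organized around it. Section 13.5 already fixes the model terms, covariance structure, degrees of freedom and decision rule, so an SAP adding the interaction would change that model and would still have to say which estimate decides.

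Two cautions on the figures also stand. They rest on the fallback covariance, not the unstructured one planned first. The average penalties for imbalance quoted under the fix come from skewed distributions, so a typical trial would fare better than the mean.

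**Conclusion.** The concern holds: section 13.5 is wrong as written. It names a primary comparison and specifies a model that cannot estimate it. That conclusion follows from the model terms alone and depends on no assumed SD. It is limited to 13.5 and the matching Synopsis text, since the separate SAP was not supplied.

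How far the choice of estimate matters depends on the assumed SD and the number of completers. With 12 completers and SD 3 cm the gap between the pooled and one-group chances is small (99.8% against 92%). With 8 completers it is 97% to 30% against 75% to 17%. Partial data from non-completers, which 13.2 keeps, may improve these figures somewhat; chance imbalance of groups over sequences would worsen them. The main loss is an unanswered primary question and an undefined decision rule, more than a high risk of a false claim.

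**What to change.** 1. Add use group (the section 8.1 definition) and treatment by group to the SDLP model. Report the cannabis-placebo difference with its 95% CI in each group, and the interaction with its CI. Define the pooled difference as the equally weighted average of the two group differences. Align section 5.1, which describes daily and weekly users, with the 8.1 definition.

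2. Before database lock, state which estimate decides the 4.4 cm rule:
   - *Pooled decides.* The frequency comparison becomes estimation only, and the Synopsis and 13.5 are reworded to match. Precision at 6-8 completers supports this choice, and the group estimates still serve the intent in 5.1.
   - *Groups decide.* State whether both must meet 4.4 cm (no alpha adjustment needed) or either may (alpha control needed, which the no-adjustment sentence in 13.5 does not cover).

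3. Label the McNemar and symmetry tests as pooled supportive analyses.

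4. With about 6 completers the group main effect can be aliased with sequence. State that the within-subject group and interaction contrasts will still be reported; with one completer per sequence they were estimable in all 20 possible 3+3 splits.

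**Cost.** Wording only; no extra subjects. Under variance components with balanced completers, two error df are lost and the pooled CI widens by 2.101/2.086 - 1 = 0.7% with 12, 2.228/2.179 - 1 = 2.3% with 8 and 2.447/2.306 - 1 = 6.1% with 6. With random drop-out and chance imbalance the average widening is 0.7%, 5.8% and 14.6%. The mean variance of the interaction rises by 12%, 29% and 53%, and of a group difference by 6%, 21% and 42%. The cost under an unstructured covariance with Kenward-Roger df was not computed. The plan should say in advance that group intervals will be wide: with 4 per group, an observed difference of 0 gives an upper limit of 3.3 to 8.9 cm.
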